5.2.6. Pharmacodynamic Bile Acids

The following are PD bile acid endpoints: total bile acids, ursodeoxycholic acid (UDCA), chenodeoxycholic acid (CDCA), lithocholate acid (LCA), cholic acid (CA), deoxycholic acid (DCA), (conjugated and unconjugated forms) and C4 in relation to the average exposure of total OCA.

- Observed values and change from Baseline will be evaluated at each DB post-Baseline visit

5.2.7. Disease Specific Symptoms

The disease specific endpoints include the following: Pruritus Visual Analogue Scale (VAS), 5-D Itch questionnaire, partial Mayo score assessment for subjects with ulcerative colitis (UC), and Crohn's disease activity index (CDAI).

- Observed values and change from Baseline will be evaluated at each DB post-Baseline visit

5.3. Exploratory Endpoints

5.3.1. Exploratory Marker of Pruritus

Pruritus will be assessed by measuring Autotaxin activity.

- Observed values, change from Baseline, at Week 12 and Week 24, will be summarized
- Correlation of Autotaxin with 5D and VAS scores at Week 12 and Week 24 will be assessed

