- i Vital signs: oral temperature, sitting heart rate (HR), respiratory rate, and sitting blood pressure ([BP] systolic and diastolic). When taking HR, respiratory rate, and BP readings, subjects should be seated quietly for a minimum of 3 minutes before the readings are taken.
- j TE: at trial sites where the Fibroscan® TE device is available. TE has a 5-day visit window. For the Day 0 assessment, TE should occur either on Day 0 or within 5 days prior to Day 0. For the Week 24 assessment, the TE should occur within  $\pm 5$  days of the onsite visit if it is not possible to schedule the TE on the same day as that visit, but the visit(s) should remain within the overall visit window.
- k Hepatic ultrasound has a  $\pm 5$ -day visit window (ie, if it is not possible to schedule the ultrasound on the same day as the onsite visit, it may occur within 5 days on either side of the visit, but the visit(s) should remain within the overall visit window).
- l Partial Mayo score completed only for subjects with UC.
- m Subjects with UC will be asked to complete a diary the day prior to their next trial visit, recording details since their last scheduled visit. Subjects with CD should complete the diary in the 7 days prior to their next clinic visit. Diary card data from the Screening period are collected at the Day 0 visit.
- n CDAI completed only for subjects with CD.
- o Questionnaire completed by the subject.
- p Adverse events will be collected from the time that signed informed consent is obtained.
- q All subjects are instructed to administer the first dose of investigational product on Day 1 and at approximately the same time of day for the duration of the trial (see [Section 8.1](#)).
- r Investigational product is dispensed only for subjects who continue into the LTSE. (Dispensing of open-label investigational product occurs after completion of the Week 24/LTSE Day 1 procedures and the subsequent unblinding of the subject's treatment allocation.)
- s Investigational product accountability/compliance will include review of tablets and bottles dispensed and returned at each clinic visit
- t All laboratory samples (except urine and serum pregnancy test, if applicable) are analyzed by the Central Laboratory.
- u IgG4 is included in the assessment panel at Screening only.

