#### Hepatic and GI Inflammation, Hepatic Disease and Fibrosis

Hepatic and GI inflammation, hepatic disease, and fibrosis will be assessed by measuring the following:

Autotaxin and its metabolites, calprotectin, C-reactive protein (CRP), Cytokeratin-18 (CK-18), ELF markers, transient elastography (TE), Immunoglobulin A (IgA), IgG, Immunoglobulin M (IgM), Interleukin-6 (IL-6), Interleukin-12 (IL-12), Interleukin-23 (IL-23), transforming growth factor-beta (TGF- $\beta$ ), tumor necrosis factor-alpha (TNF- $\alpha$ ).

The Enhanced Liver Fibrosis (ELF™) test is a blood test that measures hyaluronic acid (HA), procollagen-3 N-terminal peptide (P3NP), and a tissue inhibitor of metalloproteinase 1 (TIMP-1), as a measure of hepatic fibrosis.

Transient Elastography (TE) is an assessment of hepatic fibrosis using a Fibroscan® TE device (Echosens, Paris, France) that measures hepatic stiffness. It is a validated and non-invasive measure and will be performed at trial sites that have the equipment. Trial sites must have staff trained in the use and data interpretation of the device.

GI inflammation will be assessed by measuring fecal calprotectin in subjects who provide fecal samples.

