#### 12.3.2. Secondary Efficacy Analysis

Secondary efficacy analyses of hepatic biochemistry and function parameters (eg, ALT, AST, and GGT) will be summarized by treatment group using descriptive statistics at Baseline and at each scheduled post-Baseline visit. The change from Baseline will also be summarized. Baseline is defined as the mean of all available evaluations prior to treatment. Hepatic biochemistry and function parameters will be analyzed using the same ANCOVA model as specified for the primary efficacy analysis.

A hierarchical approach will be used for multiplicity adjustments. If the primary efficacy analysis is statistically significant ( $p < 0.05$ ), the following order will be used in the testing procedure to compare the change from Baseline in ALP between OCA and placebo:

- Week 12: OCA 5 mg treatment group (randomized to 5 mg for the initial 12 weeks followed by 10 mg for the latter 12 weeks) vs. placebo
- Week 24: OCA 3 mg treatment group (randomized to 1.5 mg for the initial 12 weeks followed by 3 mg for the latter 12 weeks) vs. placebo
- Week 12: OCA 1.5 mg treatment group (randomized to 1.5 mg for the initial 12 weeks followed by 3 mg for the latter 12 weeks) vs. placebo

If at any step a comparison above is not statistically significant, then all subsequent comparisons will be exploratory rather than confirmatory.

In addition, secondary efficacy analyses of ALP response rates, defined as ALP to  $<1.5x$  ULN, will compare OCA treatment groups and placebo at Week 12 and Week 24 using a Cochran-Mantel-Haenszel test stratified by the randomization stratification factor.

Hepatic stiffness measurements (based on TE) will be summarized by treatment group using descriptive statistics at Baseline and at each scheduled post-Baseline visit. The ELF score and its components (HA, P3NP, T1MP-1) and the other markers of fibrosis and/or inflammation will be summarized based on available data by treatment group using descriptive statistics at Baseline and at each scheduled post-Baseline visit. The change from Baseline will be analyzed using the same ANCOVA model as specified for the primary efficacy analysis.

Subgroup analyses will be evaluated as deemed appropriate, including but not limited to, those subjects who start antibiotics after first dose of investigational product.

Full details regarding the planned analyses, methods, and outputs for the trial will be included in the SAP.

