### **Biomarkers of Inflammation**

autotaxin & its metabolites

CRP

IgA

IgG

IgG4

IgM

IL-6

IL-12

IL-23

TGF- $\beta$

TNF- $\alpha$

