5.2.3. Markers of Hepatic Inflammation and Fibrosis

The following laboratory parameters will be summarized for markers of hepatic inflammation and fibrosis: calprotectin, C-reactive protein (CRP), Cytokeratin-18 (CK-18), Immunoglobulin A (IgA), Immunoglobulin G4 (IgG4), Immunoglobulin M (IgM), Interleukin-6 (IL-6), Interleukin-12 (IL-12), Interleukin-23 (IL-23), Transforming growth factor-beta (TGF- β), Tumor necrosis factor-alpha (TNF- α); and for measures of hepatic stiffness measurements obtained via Transient elastography (TE) at participating sites; and enhanced liver fibrosis (ELF) measures of hyaluronic acid (HA), procollagen-3 N-terminal peptide (P3NP), tissue inhibitor of metalloproteinase 1 (TIMP-1).

- Observed values, change from Baseline, and percentage change from Baseline will be evaluated at each DB post-Baseline visit

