9.2.3. Markers of Hepatic and GI Inflammation, Disease, and Fibrosis

The secondary efficacy parameters related to markers of hepatic and GI inflammation and disease include calprotectin, CRP, CK-18, IgA, IgG, IgM, IL-6, IL-12, IL-23, TGF- β , and TNF- α .

The secondary efficacy parameters related to measures of fibrosis include hepatic stiffness measurements obtained via TE (at participating sites), the ELF score and its components (HA, P3NP, T1MP-1).

These parameters will be analyzed using arithmetic summary statistics, ANCOVA, and model estimates with independent variables as described in [Section 6.2.3](#) for the primary efficacy endpoint.

The proportion of fibrosis improvement based on TE measurement will be summarized using arithmetic summary statistics as described in [Section 6.2.2](#) by treatment group at Week 24 of the DB phase. Fibrosis improvement rates, any improvement vs. no improvement or worsening, will compare OCA treatment groups vs. placebo at Week 24 using a Cochran-Mantel-Haenszel test stratified by the randomization stratification factor.

Fibrosis improvement will also be defined as follows:

- Any improvement (Change from Baseline <0)
- No change or Worsening (Change from Baseline equal to ≥ 0)

Calprotectin will potentially be analyzed. The details of the analysis will be specified in a separate SAP.

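### The SAP changes three secondary markers without declaring it: autotaxin has no OCA-placebo comparison, the endpoint list has IgG4 in place of IgG, and calprotectin has two conflicting plans.

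*SAP*

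**What the plan says.** **Protocol.** Section 10.3 lists the secondary measures of hepatic and GI inflammation, hepatic disease and fibrosis: "Autotaxin and its metabolites, calprotectin, C-reactive protein (CRP), Cytokeratin-18 (CK-18), ELF markers, transient elastography (TE), Immunoglobulin A (IgA), IgG, Immunoglobulin M (IgM", followed by cytokines. The synopsis table of criteria for evaluation also has autotaxin, calprotectin and IgG as secondary. Appendix A places "autotaxin & its metabolites" under biomarkers of inflammation. Section 12.3.2 summarizes ELF and the other fibrosis or inflammation markers by treatment group, then states: "The change from Baseline will be analyzed using the same ANCOVA model as specified for the primary efficacy analysis". On IgG4, a footnote to Table 1 says "IgG4 is included in the assessment panel at Screening only", and section 11.2.5 agrees.

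**SAP.** Section 5.3.1 says "Pruritus will be assessed by measuring Autotaxin activity" and plans a summary of values and change at Weeks 12 and 24, plus a correlation with the 5-D and VAS scores. Section 5.2.3 omits autotaxin, and its immunoglobulins after IgA are "Immunoglobulin G4 (IgG4), Immunoglobulin M (IgM"; it asks for change and percentage change at every post-Baseline visit. Section 9.2.3 omits autotaxin, names IgG, includes calprotectin and assigns the ANCOVA to all the markers that it lists. The same section ends: "Calprotectin will potentially be analyzed. The details of the analysis will be specified in a separate SAP". Section 11, the place for departures from the protocol, mentions only microbiome and genetic samples.

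**The concern.** SAP 5.2 presents its secondary endpoints as those the protocol defines, and Section 11 reports no marker change. A reader would conclude that the marker analyses are as in the protocol, and they are not.

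The autotaxin change matters most. A comparison between randomized arms shows whether OCA changes the marker. A correlation with itch answers a different question, and the SAP does not say whether it is pooled across arms, computed within arm or adjusted for arm. Protocol 4.5 expects OCA to worsen itch. If OCA also moves autotaxin, a pooled correlation could appear with no link between the two within any arm.

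For IgG4 the endpoint as listed cannot be computed. For calprotectin, the measure by which protocol 10.3 says GI inflammation will be assessed, two programmers could follow the same SAP section and deliver different things.

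**Working it through.** The plan gives no figure to reproduce, and the point rests on no sample size, power or alpha. The check is a comparison of lists.

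| Marker | Protocol 10.3 / 12.3.2 | SAP 5.2.3 (endpoints) | SAP 9.2.3 (ANCOVA list) | Elsewhere in SAP | Declared in SAP 11 |
|---|---|---|---|---|---|
| Autotaxin | Secondary, ANCOVA | Absent | Absent | 5.3.1: summary and itch correlation | No |
| IgG | Secondary, ANCOVA | Absent | Present | – | No |
| IgG4 | Not a secondary measure; Screening only | Present | Absent | – | No |
| Calprotectin | Secondary, ANCOVA | Present | Present | 9.2.3, last lines: optional, separate SAP | No |

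**Autotaxin.**
1. Protocol Appendix A classes it as an inflammation biomarker, so it falls within the markers covered by the ANCOVA sentence in 12.3.2.
2. SAP 9.2.3 gives the ANCOVA to its own list, and autotaxin is not on it.
3. SAP 9.3, on exploratory analyses, covers only FGF-19, so 5.3.1 is the only place that specifies an autotaxin analysis. It names no comparison between arms. It also omits the metabolites that the protocol includes.
4. On the correlation: pooled covariance = average within-arm covariance + covariance of the arm means. With the first term zero, the pooled value is still non-zero when treatment shifts the means of both variables together. A within-arm or arm-adjusted correlation removes the second term.

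**IgG4.** Change from Baseline = post-Baseline value − Baseline value (SAP 6.3.5). Screening supplies the Baseline. The double-blind schedule has post-Baseline visits at Weeks 2, 6, 12, 14, 18 and 24, with no IgG4 draw at any of them. The change is therefore undefined for every subject. SAP 9.2.3 does not ask for IgG4, so the error stops at the endpoint list.

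**Calprotectin.** Within SAP 9.2.3 the earlier text makes the ANCOVA part of this plan; the closing lines make the analysis optional and place its details in another document. Both cannot hold. The protocol has no such deferral. It does make fecal samples voluntary (Table 1 footnote) and expects them from a subset (10.1), so either plan covers fewer than all subjects.

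**The case against.** The strongest reply is that these are wording faults with no confirmatory result behind them. The hierarchy covers ALP only, SAP 6.2.7 adjusts nothing else, and protocol 12.3.2 leaves full details to the SAP, so a sponsor may reclassify a marker before database lock. That stands as far as it goes: reclassification is permissible if declared, and it was not declared.

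A second reply is that the general methods already supply an autotaxin comparison. SAP 6.2.3 describes an ANCOVA for any parameter, and 6.2.4 adds a repeated-measures model for clinical laboratory values. Neither names autotaxin, and 5.3.1 sets a narrower analysis for it, so these sections do not restore the comparison.

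Several stronger readings are tempting, and the documents do not support them:
- That the IgG analysis is lost. It is not; SAP 9.2.3 has IgG, as the protocol does.
- That silence in SAP Appendix A proves autotaxin was dropped. The titles of the inflammation tables name no individual marker, so CRP or IL-6 would fail the same test.
- That the calprotectin analysis will be chosen with unblinded data in hand. This is only a possibility. The other SAP has no stated date, but the planned interim concerns ALP, and the SAP requires post hoc analyses to be labelled.
- That the loss can be expressed as power. The documents give no autotaxin SD or expected effect, and a detectable difference in SD units would be the same for any marker at this sample size.

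**Conclusion.** The point holds for three undeclared inconsistencies of unequal weight. Autotaxin is the substantive one: following the SAP as written drops a randomized comparison that the protocol specifies for a secondary marker. The IgG4 entry is a slip confined to SAP 5.2.3, and the calprotectin conflict is internal to SAP 9.2.3. All three should be corrected. None touches the primary ALP analysis, the testing hierarchy, alpha or the sample size.

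The conclusion assumes that the ANCOVA sentence in protocol 12.3.2 covers the inflammation markers named just before it, which is the natural reading. It also assumes that autotaxin is assayed at Day 0, Week 12 and Week 24. Table 1 does not name it, but has a row for ELF markers and other analytes at those visits, and SAP 5.3.1 expects values at Weeks 12 and 24. Whether OCA shifts autotaxin is not known from the documents; the remark on the correlation concerns what an unspecified method could show.

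**What to change.** 1. **Autotaxin.** Add it, with its metabolites if assayed, to SAP 5.2.3 and 9.2.3. Apply the 6.2.3 ANCOVA to the Week 12 and Week 24 change and report it in existing Tables 14.2.5.1 and 14.2.5.2. In 5.3.1, specify that the correlation with itch is computed within arm or adjusted for arm. If the reclassification is intended, declare it in Section 11 with the reason.
2. **IgG4.** Replace it with IgG in SAP 5.2.3.
3. **Calprotectin.** State one plan before unblinding. The default is the protocol's ANCOVA, limited to subjects who gave fecal samples, with the number contributing in each arm shown; the closing deferral in 9.2.3 then goes. If the sponsor prefers a separate plan, take calprotectin off the ANCOVA list, finalize that plan before unblinding and record the change in Section 11.

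The cost is SAP wording and one more analyte in an existing table program. No new visit or sample is needed if autotaxin is assayed from the scheduled blood draws, which should be confirmed against the laboratory manual. No alpha is spent.

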6. GENERAL ANALYSIS CONSIDERATIONS

6.1. Data Reporting

The statistical analyses will be reported using summary tables, figures, and data listings.

Laboratory units will be summarized and presented both in conventional units (CV) and in the international system of units (SI).

Individual subject data obtained from the electronic case report forms (eCRFs), external laboratory data, and any derived data (such as change from Baseline and percent change from Baseline) will be presented in data listings by subject. Data from all assessments, whether scheduled or unscheduled, will be listed by subject and visit. Unscheduled visits and visits occurring more than one day outside protocol defined window will not be included in the table summaries, excluding transient elastography measurements.

The analyses described in this plan are considered a priori, in that they have been defined prior to database lock of the DB phase. Post hoc analyses will be labeled as such on the outputs and identified in the CSR.

All analyses and tabulations will be performed using SAS® Version 9.2 or higher. PK parameters will be estimated using Phoenix® WinNonlin® Version 6.3. The following processes will be employed to validate statistical outputs: derived datasets (both tabulation datasets and analysis datasets), summary tables, and data listings will be verified through independent programming; graphical displays will be compared against supporting summary tables; and all outputs will undergo a senior-level statistical review. The process includes confirmation that statistically valid methods have been implemented and that all data manipulations and calculations are appropriate and accurate. Checks will be made to ensure accuracy, adherence to this SAP, consistency within tables, and agreement between tables and their corresponding data listings. Upon completion of validation/verification and quality review procedures, all documentation will be collected and filed in the study master file by the project statistician or designee.

6.2. Data Analysis and Summaries

Data distribution characteristics will determine which analysis methods are most appropriate. If methods do not allow for parametric modeling assumptions to be met, then non-parametric methods will be implemented.

6.2.1. Arithmetic Summaries

Continuous variables will be summarized by means, standard deviations (SDs), standard errors of the mean (SEMs), medians, interquartile range (IQR), minimums, and maximums.

6.2.2. Categorical Methods

Categorical variables will be summarized by counts and percentage of subjects in corresponding categories. Percentages will be based on the number of non-missing assessments unless otherwise specified.

6.2.3. Analysis of Covariance

Analysis of covariance (ANCOVA) will be performed to provide least square (LS) mean estimates and 95% two-sided confidence intervals (CIs) of the change and percentage change from Baseline at each DB post-Baseline visit. Model covariates include then randomization stratification values (ie, UDCA use [yes, no] and screening total bilirubin [$\leq 1.5 \times \text{ULN}$, $> 1.5 \times \text{ULN}$ – $< 2.5 \times \text{ULN}$]) and the Baseline of the parameter being estimated. The primary analysis will exclude the treatment by visit interaction term.

Normality/Equal Variance Testing

The assumption of a random error component being normally distributed will be tested by examining skewness and kurtosis following D'Agostino et al. (1990) with the residuals pooled over treatments. Additionally, homogeneity of variances across treatment groups will be examined using Levene's Test (Glaser 1982) with significance level of 0.05, based on absolute values of the residuals from the residual medians for each treatment. The data will be determined non-normal if the p-value for either the D'Agostino Skewness Test or D'Agostino Kurtosis Test is less than 0.05. If the data do not meet the normality or homogeneity assumptions of the parametric analyses, then a RT-2 rank transformation will be applied to the data (CFB endpoint and baseline value). To minimize the effect of differing study site sizes, the ranks will be standardized to lie between 0 and 1 using the NPLUS1 option of SAS® PROC RANK. Tied values will receive the mean value (midranks) of the corresponding ranks.

Example SAS® code for the primary analysis is as follows:

```
ODS graphics on;  
proc mixed data=ADLB noclprint plots=residualpanel;  
  class ucdafl tbilfl trt;  
  model change=Baseline ucdafl tbilfl trt / ddfm=kr;  
  lsmeans trt / cl diff alpha=0.05;  
  title1 "Linear Mixed Effects Model Based Estimates of XXXX Means";  
  title2 " Fixed Effects for Visit, Randomization Strata, and Treatment and Baseline as  
  Covariates";  
run;  
ODS graphics off;  
quit;
```

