3. STUDY DESIGN AND PLAN

This is a Phase 2, randomized, double-blind, placebo-controlled, dose-finding evaluation of the efficacy and safety of OCA in subjects with PSC. The trial design is shown in [Figure 1](#). Approximately 75 subjects who provide written informed consent and meet all of the inclusion

and none of the exclusion criteria will be randomized to 1 of 3 treatment groups as follows: 1.5 mg titrating to 3 mg OCA, 5 mg titrating to 10 mg OCA, or placebo in a 1:1:1 ratio. Subjects will administer investigational product orally, once daily for 2 consecutive 12-week periods. Randomization will be stratified by the presence or absence of concomitant UDCA use and total bilirubin level ($\leq 1.5 \times \text{ULN}$ or $> 1.5 \times \text{ULN}$ but $< 2.5 \times \text{ULN}$). No more than 50% of subjects randomized will be administering UDCA at the time of randomization.

[figure not shown]
For the first 12 weeks after randomization, the subject's dose will be 1.5 mg OCA, 5 mg OCA, or placebo. After 12 weeks, the subject's dose will be titrated – 1.5 mg OCA titrating to 3 mg OCA and 5 mg OCA titrating to 10 mg OCA – and DB treatment will continue for a further 12 weeks at that dose.

Subjects will have a screening period of up to 30 days prior to Randomization/Day 0. Subjects will attend on site clinic visits at Weeks 2, 6, 12, 14, 18, and 24. The final visit during the DB phase will occur at Week 24, after which subjects will be asked to reconfirm their consent for participation in the LTSE phase (a further 24 months).

Upon a subject's completion of the DB phase, the trial blind will be broken in order to assign the starting OCA dose for the LTSE phase. It is intended that subjects will commence treatment at 5 mg OCA, except those subjects who completed treatment in the DB phase with 10 mg OCA who will continue at 10 mg OCA unless safety and tolerability warrant a dose reduction to 5 mg. The titration schedule and options for the LTSE phase are detailed in the protocol.

The overall study duration is up to 32 months, including up to a 30-day Screening period, 6 month DB period, followed by a 24-month open-label LTSE period, and a 1-month follow-up period. The LTSE may be extended as determined by the sponsor via protocol amendment and regulatory and Institutional Review Board/Independent Ethics Committee review and approval.

Figure 1: Study Design Schematic

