6.2.5. Median and Confidence Interval Estimation Methods

Hodges Lehmann estimation will be used to provide estimators of the median difference and 95% CIs for the median difference.

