9.1. Primary Efficacy Analyses

The primary efficacy endpoint is the Week 24 change from Baseline in ALP. Using the ITT population, the primary efficacy analysis will compare the Week 24 change from Baseline in ALP between OCA 10 mg treatment group and placebo and OCA 3 mg treatment group and placebo using an ANCOVA model with treatment group, visit, and randomization strata as fixed effects, and Baseline ALP as a covariate.

In order, to provide estimates of the change from Baseline and corresponding 95% CI, the repeated measures ANCOVA methods described in [Section 6.2.3](#) will be applied. Model fit will be assessed in order to determine the validity of the estimates. The analysis will be repeated with percentage change from Baseline as the dependent variable. Estimates of least-square (LS) means, SEs, and 95% CIs will be presented by treatment group.

The values, change from Baseline, and percentage change from Baseline will be summarized using observed values by treatment group and visit using arithmetic summary statistics as described in [Section 6.2.1](#).

A hierarchical approach will be used for multiplicity adjustment across the primary efficacy endpoint for other visits and doses as described below. If the primary efficacy analysis is statistically significant ($p < 0.05$), the following order will be used in the testing procedure to compare the change from Baseline in ALP between OCA and placebo:

- Week 12: OCA 5 mg treatment group (randomized to 5 mg for the initial 12 weeks followed by 10 mg for the latter 12 weeks) vs. placebo
- Week 24: OCA 3 mg treatment group (randomized to 1.5 mg for the initial 12 weeks followed by 3 mg for the latter 12 weeks) vs. placebo
- Week 12: OCA 1.5 mg treatment group (randomized to 1.5 mg for the initial 12 weeks followed by 3 mg for the latter 12 weeks) vs. placebo

If at any step a comparison above is not statistically significant, then all subsequent comparisons will be exploratory rather than confirmatory.

Sensitivity analysis for the primary efficacy analysis will be performed using the W12C and W24C Populations. In addition, the arithmetic summary statistics will be presented by antibiotic use, IBD, UC, and CD subgroups as described in [Section 6.2.8](#).

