An unblinded interim analysis of the primary endpoint will be conducted after approximately 50% of the subjects have completed the initial 12-weeks of blinded treatment. The interim analysis will use the same model described in [Section 6.2.3](#) on the change from Baseline ALP to Week 12 in addition to Week 24.

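### Does SAP 6.2.3 put the primary test at risk by not saying over which subjects the fallback ranks are formed?

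*SAP*

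**What the plan says.** SAP Section 6.2.3 tests the ANCOVA residuals for skewness, kurtosis and unequal variances, each at 0.05. It then provides: "If the data do not meet the normality or homogeneity assumptions of the parametric analyses, then a RT-2 rank transformation will be applied". The sentence goes on to name the two variables to be transformed, the change from Baseline and the Baseline value. The next sentence gives the scaling and its reason: "To minimize the effect of differing study site sizes, the ranks will be standardized to lie between 0 and 1", by means of the NPLUS1 option of PROC RANK. Ties receive midranks.

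The example code in the same section has the model line "model change=Baseline ucdafl tbilfl trt / ddfm=kr". It contains no site term and no ranking step, and its CLASS statement lists only the two strata and treatment. SAP Section 3 names the stratification factors: "Randomization will be stratified by the presence or absence of concomitant UDCA use and total bilirubin level". Site is not one of them. Section 9.1 carries the same model into the unblinded interim: "The interim analysis will use the same model described in" Section 6.2.3.

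**The concern.** A rank transformation is not fully specified until the ranking set is known. Here the text states none and does not explain RT-2, and the reason given for the scaling points somewhere odd. Dividing by N+1 can offset differing site sizes only if ranks are formed separately in each site. A literal-minded programmer might therefore add a BY site statement.

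That would matter. About 35 sites are planned (Protocol Synopsis), so a typical site would hold two subjects and the ranks would carry little information about the size of an ALP change. The p-value concerned is the primary one, and three further ALP comparisons are tested only if it is significant (SAP 6.2.7).

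**Working it through.** **Inputs.** From SAP Section 4: 25 subjects per arm, mean changes -20 and -5 (difference 15), SD 16, two-sided alpha 0.05, 20% dropout. From the Protocol Synopsis: about 35 sites. Site sizes are not in the documents and are assumed.

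**1. The plan's own figure.** Noncentrality is 15 / (16 × √(2/n)).
- n = 25: 15 / 4.525 = 3.315 on 48 df, power 0.901. The stated 90% reproduces with 25 evaluable per arm.
- n = 20 (25 less 20%): 15 / 5.060 = 2.965 on 38 df, power 0.824.

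**2. The scaling under pooled ranks.** Change and Baseline ranks are each multiplied by the constant 1/(N+1), which is 1/76 for N = 75. The treatment coefficient and its standard error both shrink by that factor, so t and p do not move. The site-size sentence is inert under this reading.

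**3. The ranks under a within-site reading.** There are 75/35 = 2.14 subjects per site on average. A sole subject gets 1/(1+1) = 0.5. A pair gets 1/3 and 2/3, however large or small the ALP changes are.

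**4. Simulated power of the whole procedure.** The simulation used a three-arm ANCOVA with UDCA, bilirubin and Baseline. The skewness, kurtosis and Levene tests ran on the residuals, and if any had p < 0.05 the model was refitted to midranks/(n+1). The contrast is OCA 10 mg against placebo. Assumptions: normal errors, 16 as the residual SD, UDCA use 50%, raised bilirubin 20%, no site effects. Runs: 4000 at 25 per arm (Monte Carlo SE √(0.9 × 0.1 / 4000) = 0.005) and 3000 at 20 per arm (√(0.81 × 0.19 / 3000) = 0.007).

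| | 25 evaluable per arm | 20 evaluable per arm |
|---|---|---|
| Fallback fires | 11.5% | 12.2% |
| Unranked ANCOVA throughout | 0.899 | 0.811 |
| Procedure, pooled ranks | 0.900 | 0.812 |
| Procedure, within site, 35 even | 0.849 | 0.750 |
| Procedure, within site, 35 random | 0.856 | 0.760 |
| Procedure, within site, 35 skewed | 0.878 | 0.778 |

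Arithmetic check for 25 per arm and even sites: among trials in which the fallback fires, power is 0.902 pooled and 0.462 within site. The loss is 0.115 × (0.902 - 0.462) = 0.051, and 0.900 - 0.051 = 0.849, as tabulated.

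**5. Which reading the text supports.**
- For pooled ranks: no BY group is named. Site appears in neither the model line, the CLASS statement nor the strata. The transformation is applied to two named variables, which fits ranking each of them once over all subjects.
- For within-site ranks: one clause that gives a reason for the scaling. It describes a purpose and does not instruct anyone to rank by site. Step 3 shows that following it that way would produce nearly uninformative ranks, which any statistician would notice.

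**The case for a change.** The strongest opposing case has three parts.

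First, a sentence in an analysis plan should be presumed to do something, and this one does something only with by-site ranks. Section 6.1 promises that "Checks will be made to ensure accuracy, adherence to this SAP", yet a check against the text cannot choose between two programs that the text might both allow. It is true that the sentence has no function under pooled ranks. But Section 6.1 also requires independent programming of datasets and tables and a senior statistical review. A lone by-site ranking would show up as a mismatch and have to be explained.

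Second, normal data are the mildest case. ALP at entry has a floor of 2 × ULN and no ceiling, and the endpoint is an absolute change, so non-normal residuals are plausible. With t(4) errors the fallback fires in 65% of trials, and power is 0.954 pooled against 0.717 to 0.850 within site over the three 35-site patterns. With lognormal-type errors it fires in 98%, with 0.98 against 0.682 to 0.860. These figures stand, but every loss belongs to the within-site reading. In the same runs pooled ranks beat the unranked ANCOVA (0.954 against 0.891, and 0.98 against 0.885). The fallback, read plainly, does what it is there for.

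Third, the unblinded interim uses the same model, so the reading might first be settled with treatment codes in hand. Simulated type I error when the reading is chosen at the interim was 0.047 to 0.058, against 0.048 to 0.060 for readings fixed beforehand. That run assumed 38 subjects and a Week 12 to Week 24 correlation of 0.7. It covered only normal data and changes proportional to a Baseline with a CV of 30%. The Protocol describes the interim as being for planning, with no stop for futility.

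**Conclusion.** The wording is loose, but this is a gap that analysts fill sensibly. The model, code and strata all point to one ranking over all analysed subjects. Under that reading the primary procedure keeps the power of the unranked ANCOVA: 0.900 against 0.899 at 25 evaluable per arm, and 0.812 against 0.811 at 20.

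The loss would be 2 to 5 points (0.900 to between 0.878 and 0.849) at 25 evaluable per arm, and 3 to 6 points (0.812 to between 0.778 and 0.750) at 20. It arises only if someone ranks by site, which the text does not direct. Those losses rest on assumed site sizes over 35 sites and on normal data; they would be larger with heavy-tailed or skewed changes.

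Type I error is about nominal (0.048 to 0.060 in simulation) under any reading fixed in advance. Naming the ranking set or removing the site-size remark would alter no number in a pooled analysis, so no change to the plan is called for.
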